12.7.1 Objective Disease Response

Descriptive statistics (frequency and percentage) for ORR and iORR, and the two-sided exact 95% Clopper-Pearson confidence interval⁽⁴⁾ (CI) for the iORR/ORR will be presented for patients with measurable disease in each indication separately. Primarily, patients with missing data will be considered to be non-responders.

Sensitivity analyses on iORR and ORR will be performed including the use of:

- ASaT and PP populations
- No imputation of missing data (i.e. only patients with evaluable post-baseline tumor assessment)

12.7.2 Tumor Burden

A summary table of tumor burden by scheduled assessment window will be presented along with an accompanying listing. A waterfall plot of maximum percent reduction in the sum of diameter of target lesions from baseline will be created for each indication separately. These plots will display the best percentage CFB in the sum of the diameter of all target lesions for each patient.

A spaghetti plot of percent reduction in the sum of target lesions from baseline will be created to plot the change in tumor burden over time (in weeks from start of treatment) for each patient.

A swimmer plot showing an overview of tumor assessments in relation to treatment exposure, follow up and treatment status (ongoing/stopped) will be created.

12.7.3 BOR and iBOR

BOR/iBOR will be summarized using descriptive statistics (frequency and percentage) for each indication separately.

Additionally, BOR will also be explored as per PCWG3-modified RECIST 1.1 for patients in mCRPC, with both measurable and non-measurable disease.

A sensitivity analysis will be performed for BOR and iBOR using the ASaT and Per Protocol populations.

12.7.4 DOR and iDOR

DOR/iDOR will be summarized using Kaplan-Meier estimates for each indication separately. Log-log 95% confidence intervals for estimates of the percentiles will be presented.

Responders will be considered to have an ongoing response if they: i) have not progressed, and ii) have not started a new anti-cancer therapy, and iii) have not been lost to follow-up, and iv) are alive.

Patients with missing data will be censored/considered as having an event as specified below:

Situation	Date of progression or censoring	Outcome
No progression, no death. No start of new anti-cancer therapy.	Date of the last evaluable tumor assessment.	Censored
No progression, no death. Start of new anti-cancer therapy.	Date of the last tumor assessment with non-progression before the start of new anti-cancer therapy.	Censored

Situation	Date of progression or censoring	Outcome
Progression or death after one missed adequate tumor assessment.	Date of progression or death, whichever is earliest (if both occur).	Progressed
Progression or death after more than one (consecutively) missed adequate tumor assessments.	Date of the last evaluable tumor assessment.	Censored

DOR will be calculated based on RECIST 1.1, iRECIST, and PCWG3-modified RECIST for the mCRPC cohort only for those patients with measurable disease at baseline.

12.7.5 CBR and iCBR

CBR/iCBR will be summarized using descriptive statistics (frequency and percentage) together with a 95% CI for each indication separately.

CBR will be calculated based on PCWG3-modified RECIST for the mCRPC cohort separately for those patients with measurable disease at baseline and for all mCRPC patients.

Primarily, patients with missing data will be considered to be non-responders.

A sensitivity analysis will be performed for CBR and iCBR using the ASaT and Per Protocol populations; and without imputing for missing response.

12.7.6 PFS and iPFS

PFS/iPFS will be summarized using Kaplan-Meier estimates for each indication separately. A sensitivity analysis will be performed using the ASaT population.

PFS will be calculated based on PCWG3-modified RECIST for the mCRPC cohort for those patients with both measurable and non-measurable disease.

Patients with missing data will be censored/considered as having an event as specified below:

Situation	Date of progression or censoring	Outcome
Incomplete or no baseline tumor assessments.	Date of the first day of study treatment	Censored
Start of new anti-cancer therapy.	Date of the last tumor assessment with non-progression before the start of new anti-cancer therapy.	Censored
Death before the first disease progression assessment.	Date of death.	Progressed

Situation	Date of progression or censoring	Outcome
Death between adequate tumor assessment visits.	Date of death.	Progressed
Progression or death after one (consecutively) missed adequate tumor assessment ^a .	Date of progression or death, whichever is earliest (if both occur).	Progressed
Progression or death after more than one (consecutively) missed adequate tumor assessments.	Date of the last evaluable tumor assessment.	Censored
No progression, no death.	Date of the last evaluable tumor assessment, or first date of study treatment if no post-baseline tumor assessments.	Censored

^aIdentified as 12 weeks between the date of last evaluable tumor assessment and the date of the event.

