#### Disease characteristics

4. Patients with the following histologically or cytologically confirmed solid tumor indications and line of treatment:
  - NSCLC
    - For the second-line or third-line treatment of patients with advanced and/or metastatic NSCLC with disease progression on or after an immune checkpoint inhibitor-containing regimen and a platinum-containing regimen, with no EGFR or ALK genomic tumor aberrations, and who are not amenable to curative treatment
  - Colorectal cancer
    - For the first-line treatment of patients with unresectable or metastatic MSI-H/dMMR colorectal cancer
  - cSCC
    - For the first-line treatment of patients with recurrent or metastatic cSCC or second line if refractory or relapsed after an immune checkpoint inhibitor-containing regimen, and in whom radiotherapy is not feasible (based on data from study SC103 [AURELIO-03])
  - Advanced hepatocellular carcinoma (not applicable in France)
    - For the second- to fourth-line treatment of patients with advanced hepatocellular carcinoma having progressed on or after a checkpoint inhibitor-containing regimen
  - mCRPC
    - For the second- to fifth-line treatment of patients with mCRPC after recurrence or failure of docetaxel and prior treatment with abiraterone, enzalutamide, or any other androgen receptor-targeted agent
  - Ovarian cancer
    - For the second- to fifth-line treatment of patients with advanced ovarian cancer after recurrence or failure on the last platinum-based therapy within 6 months
5. Have measurable disease per RECIST 1.1 as assessed by the local site investigator/radiology; lesions situated in a previously irradiated area are considered measurable if progression has been demonstrated in such lesions

mCRPC: Patients with both measurable and non-measurable disease will be enrolled. At least 35 patients with measurable disease will be enrolled. Patients with no measurable disease and only widespread bone disease must have a CTC count of  $\geq 5$  cells per 7.5 mL of blood.

6. Availability of tumor tissue from a fresh biopsy at screening unless the biopsy cannot be obtained due to safety reasons or non-accessibility of the tumor site. If it is not possible to obtain a fresh biopsy, every effort should be taken to retrieve an archival biopsy. Archived, fixed tumor tissue may only be collected if taken preferentially after completion of the most recent systemic tumor therapy and within 12 months prior to the first dose of study treatment.

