#### **8.1.1.3 End of treatment and follow-up tumor imaging**

If patients discontinue study interventions, tumor scans should be performed at the time of discontinuation ( $\pm 4$ -week window) unless previous scans were obtained within 4 weeks of discontinuation. If patients discontinue study interventions due to documented disease progression, this is the final required tumor scan if the investigator elects not to implement iRECIST.

---

If patients discontinue study interventions without documented disease progression, every effort should be made to monitor disease status by acquiring tumor scans using the same schedule used while on treatment (every 6 weeks [ $\pm$ 2 weeks]).

Scans are to be continued until one of the following conditions are met:

- Disease progression identified by the investigator (radiological progression per [i]RECIST [1.1] or mCRPC-specific progression)
- Start of a new anti-cancer treatment
- Pregnancy of the patient
- Withdrawal of consent by the patient
- End of the study

For clinically unstable patients, a scan obtained within 2 weeks after clinical progression is recommended. Scans are to be continued as per regular schedule (section [1.3](#)).

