PFS and iPFS are defined as the time from the first day of study treatment until the first date of radiological disease progression or death and will be summarized using Kaplan-Meier estimates for each indication separately.

Patients with missing data will be censored/considered as having an event as specified below:

Situation	Date of progression or censoring	Outcome
Incomplete or no baseline tumor assessment	Date of the first day of study treatment	Censored
Start of new anti-cancer therapy	Date of the last tumor assessment with non-progression before the start of new anti-cancer therapy	Censored
Death before the first disease progression assessment	Date of death	Progressed
Death between adequate tumor assessment visits	Date of death	Progressed
Progression or death after one missed adequate tumor assessment	Date of progression or death, whichever is earliest (if both occur)	Progressed
Progression or death after more than one missed adequate tumor assessment	Date of the last evaluable tumor assessment	Censored
No progression, no death	Date of the last evaluable tumor assessment	Censored

- TtR and iTtR

TtR and iTtR are defined as the time from the first day of study treatment until the first date of partial response (PR, iPR) or complete response (CR, iCR) and will be summarized using Kaplan-Meier estimates for each indication separately. Patients with missing data will be censored at the last assessment date, date of death, or date of the first day of study treatment (if incomplete or no baseline tumor assessments), whichever occurs latest.

- CTC count conversion from  $\geq 5$  to  $< 5$  cells per 7.5 mL of blood

The CTC response is defined as the proportion of patients with CTC count conversion from  $\geq 5$  to  $< 5$  cells per 7.5 mL of blood and will be analyzed and presented as a point estimate and a 95% CI for the mCRPC indication. Patients with missing data will be considered as non-responders.

- Confirmed PSA decline of  $\geq 50\%$

The PSA response is defined as the proportion of patients with a PSA decline of  $\geq 50\%$  and will be analyzed and presented as a point estimate and a 95% CI for the mCRPC indication.

Responses will need confirmation by a second consecutive value obtained 4 or more weeks after the first value indicated a response. Response will be evaluated 6 months post trial entry. Evaluable patients with no confirmed response as defined above will be classified as non-responders.

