10.13 Derivation of Efficacy Variables

Tumor assessments will be performed by investigators and assessed per iRECIST⁽¹⁾ for all tumor indications with the exception of patients in the mCRPC indication who will be assessed using iRECIST and Prostate Cancer Clinical Trials Working Group 3 (PCWG3)-modified RECIST 1.1⁽²⁾.

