10.13.1 RECIST 1.1 Response Assessment

Up to the first unconfirmed progressive disease (iUPD), the RECIST 1.1 disease response assessment will be derived from the iRECIST response assessment form as follows:

iRECIST	RECIST 1.1
iCR	CR
iPR	PR
iSD	SD
iUPD	PD
Non-iCR/Non-iUPD	Non-CR / Non-PD
NE	NE
NED	NED

After the first iUPD, the RECIST 1.1 overall response will no longer be derived.

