10.13.2 PCWG3-modified RECIST 1.1 Response Assessment

Patients with mCRPC, tumor response as per the PCWG3-modified RECIST 1.1 will be derived from the iRECIST assessment for soft tissue, and the PCWG3 bone assessment. The assessment responses for soft tissue response (according to RECIST 1.1 criteria, after derivation from iRECIST) and bone response (according to PCWG3 criteria) will be combined to give an overall radiological objective response per assessment in mCRPC indication cohort patient per PCWG3-modified RECIST 1.1. The PCWG3-modified RECIST 1.1 disease response assessment will be derived from the Disease Response CRF form as follows.

Soft Tissue Response from above derivation (RECIST 1.1)	Bone Scan result (PCWG3)	PCWG3-modified RECIST 1.1 Response
PD	Any	PD
Any	PD	PD
Any (except PD)	PDu	PDu
NE	Non-PD, NED, or NE	NE

Soft Tissue Response from above derivation (RECIST 1.1)	Bone Scan result (PCWG3)	PCWG3-modified RECIST 1.1 Response
SD	Non-PD, NED, or NE*	SD
Non-CR / Non-PD	Non-PD, NED, or NE*	Non-CR / Non-PD
PR	Non-PD, NED, or NE*	PR
CR	Non-PD or NE*	PR (if target lesions were present at baseline) Non-CR / Non-PD (if no target lesions at baseline)
CR	NED	CR
NED	NE	NE
NED	Non-PD	Non-CR / Non-PD
NED	NED	NED

*If the bone scan is entirely missing or was not done then the overall response is NE

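### In mCRPC, RECIST 1.1 PFS and iPFS are derived from soft tissue but not limited to measurable disease, so most patients who progress first in bone are informatively censored, and no PFS version is named as the main one

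*SAP*

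**What the plan says.** SAP 10.13 sets the mCRPC cohort apart as "patients in the mCRPC indication who will be assessed using iRECIST and Prostate Cancer Clinical Trials Working Group 3 (PCWG3)-modified RECIST 1.1". SAP 10.13.1 states that, up to the first unconfirmed progression, "the RECIST 1.1 disease response assessment will be derived from the iRECIST response assessment form as follows". SAP 10.13.2 then says that "tumor response as per the PCWG3-modified RECIST 1.1 will be derived from the iRECIST assessment for soft tissue, and the PCWG3 bone assessment". Its table heads the mapped RECIST 1.1 result as the soft-tissue response, and bone progression turns only the PCWG3-modified column into PD.

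SAP 7.4 lists three versions of PFS: RECIST 1.1, iRECIST and, for mCRPC only, PCWG3-modified. Of the first two, SAP 12.7.6 says that "PFS/iPFS will be summarized using Kaplan-Meier estimates for each indication separately". It then plans PCWG3-modified PFS for mCRPC patients with measurable and non-measurable disease. No version is named as the main one. By contrast, ORR, BOR and TtR are limited to measurable disease, and SAP 12.7.4 limits DOR in mCRPC in the same way.

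Protocol 5.1 (criterion 5) allows mCRPC patients without measurable disease, with the condition that "At least 35 patients with measurable disease will be enrolled". Protocol 8.1.1.3 includes among the reasons to stop scanning "Disease progression identified by the investigator (radiological progression per [i]RECIST [1.1] or mCRPC-specific progression".

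**The concern.** If bone progression is not an event for RECIST 1.1 PFS or iPFS but does end the scans, these patients leave follow-up because they have progressed, yet the two curves record them as progression-free at their last scan. Kaplan-Meier assumes that a censored patient has the same outlook as those still followed, and here that fails by construction. The curves are pushed upward, most of all for bone-only patients, whose only route to radiological progression is a new soft-tissue lesion.

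The mCRPC results would then hold up to three PFS curves that disagree in the same patients, with no rule on which to read. SAP 6.1 adds PCWG3-modified versions of BOR and CBR to show the effect of bone progression, but says nothing similar about PFS.

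**Working it through.** The documents give no PFS assumption, event count or median for mCRPC, so there is no figure to reproduce. The check traces the derivation and then illustrates its effect.

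**1. One record followed through the rules.** Take a bone-only patient with no soft-tissue disease at weeks 6, 12 and 18, and bone progression at week 12 confirmed at week 18. Scanning then stops.
- PCWG3-modified PFS: event (SAP 10.13.2, any soft-tissue result with bone PD gives PD).
- RECIST 1.1 PFS: no PD on the soft-tissue assessment. With no death, SAP 12.7.6 censors at week 18.
- iPFS: the same. The rule on stopping treatment for clinical instability applies only after an iUPD, and SAP 10.13.8 says clinical deterioration alone is not progression.
- New anti-cancer therapy: censored at the last non-progression assessment before it.
- Death: the 12-week footnote to SAP 12.7.6 puts the limit at week 18 + 12 = week 30. Without new therapy, death at week 24 is an event; death at week 34 is censored back to week 18.

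A measurable patient with stable soft tissue whose first progression is in bone is handled the same way.

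**2. How many patients.** Planned mCRPC size is 51 (SAP 8.1) and the measurable minimum is 35 (Protocol 5.1). Non-measurable maximum = 51 − 35 = 16, and 16/51 = 31.4%. Bone-only patients are a subset, since SAP 10.13.2 also has a Non-CR/Non-PD soft-tissue row. SAP 6.1 records that recruitment stopped after the August 2023 futility analysis, so the actual number is probably smaller.

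**3. Illustration under assumed hazards.** None of the medians below comes from the documents. The simulation used exponential times, scans every 6 weeks that stop at bone progression, deaths counted up to 12 weeks after the last scan, and a 24-month cutoff. It ignored confirmation of bone progression and new therapy.

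| | A | B | C |
|---|---|---|---|
| Bone-only patients | 16/51 | 16/51 | 8/51 |
| Bone-only: median to bone PD (months) | 3 | 4 | 4 |
| Bone-only: median to new soft-tissue lesion | 24 | 12 | 24 |
| Measurable: median to bone PD | 6 | 8 | 12 |
| Measurable: median to soft-tissue PD | 4 | 4 | 4 |
| All: median to death | 15 | 12 | 10 |
| Bone-only with an event, soft-tissue PFS | 37% | 53% | 51% |
| Bone-only with an event, PCWG3-modified | >99% | >99% | >99% |
| Cohort median, soft-tissue PFS (months) | 4.14 | 4.14 | 3.47 |
| Cohort median, PCWG3-modified (months) | 2.76 | 2.76 | 2.76 |
| Difference (months) | 1.38 | 1.38 | 0.71 |

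One scan interval is 42/30.4375 = 1.38 months, so these shifts are at most one interval on a coarse grid.

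**4. Why no single figure should be quoted.** Suppose both groups share one exponential hazard with a true median of 4.0 months, and a share f of first events is in bone and is lost. Then apparent median = 4.0 / [0.314(1 − f_nm) + 0.686(1 − f_m)], where nm is non-measurable and m is measurable.
- f_nm = 0.70, f_m = 0: 4.0/0.780 = 5.1 months.
- f_nm = 0.85, f_m = 0: 4.0/0.733 = 5.5 months.
- f_nm = 0.85, f_m = 0.30: 4.0/0.527 = 7.6 months.

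This formula gives no credit for deaths counted after bone progression and uses the maximum of 16 patients, so it overstates. The answer depends almost wholly on inputs with no source.

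**The case against.** The strongest reply is that SAP 12.7.6 already plans PCWG3-modified PFS for measurable and non-measurable mCRPC patients. Bone progression is therefore captured, and the side-by-side curves would show the discrepancy. This stands, and it limits the harm. The sentence can even be read as replacing RECIST 1.1 PFS in mCRPC. SAP 7.4 lists both, however, and iPFS has no PCWG3 counterpart, so iPFS is affected on either reading.

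Second, the soft-tissue reading rests on SAP 10.13.2. Protocol 9.3.1 lists bone scans among the modalities for tumor response, and Protocol 10.2.2 counts non-target progression and new lesions without excluding bone. The CRF, which could show whether bone lesions reach the iRECIST form, is not among the documents. The SAP wording is nonetheless clear enough to be programmed as soft tissue only.

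Third, reporting for the whole cohort is inferred from the absence of a restriction, and the coding of bone-only patients as having no soft-tissue disease is inferred from table rows. Neither is stated outright.

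Two stronger readings are tempting. A reader might infer that bone-only patients can hardly have a PFS event. That fits radiological progression, but not PFS, because deaths in the window and new soft-tissue lesions count. A reader might also infer that the SAP breaks the Protocol 9.3.3.2 definition, "PFS and iPFS are defined as the time from the first day of study treatment until the first date of radiological disease progression or death". Protocol section 3 lists PFS separately by RECIST 1.1, iRECIST and PCWG3-modified criteria, so some difference in how bone is handled is to be expected.

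**Conclusion.** The point holds in limited form. On the SAP's own derivation, RECIST 1.1 PFS and iPFS in mCRPC do not count bone progression, carry no measurable-disease limit, and censor most bone-first progressors because of their progression. Both curves are biased upward. PCWG3-modified PFS is not affected.

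The direction follows from the text, provided bone lesions are kept off the iRECIST form as SAP 10.13.2 implies. The size does not. The only document-based figure is the ceiling of 16 of 51 non-measurable patients at planned size. A reader might infer a definite inflation of the median, but the documents support none, and the calculated shifts are illustrations. Severity is low to moderate: PFS is secondary and descriptive, one of six cohorts is concerned, and ORR and the futility rules are untouched.

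**What to change.** In SAP 12.7.6 and 10.13.8:
- name PCWG3-modified PFS as the main PFS for the full mCRPC cohort;
- limit mCRPC RECIST 1.1 PFS and iPFS to patients with measurable disease at baseline, matching the DOR rule in SAP 12.7.4;
- label those two as soft-tissue only, with bone progression not counted;
- record the change in SAP 6.1.

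Do not redefine RECIST 1.1 PFS or iPFS to include PCWG3 bone progression. That would duplicate PCWG3-modified PFS under another name and remove the contrast that the SAP uses for BOR and CBR.

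The cost is wording and a population flag; the bone assessments are already collected and derived. The downside is that two secondary curves cover fewer mCRPC patients. Measurable patients who progress first in bone will still be censored in them, which is why the label is needed as well as the restriction.

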#### **8.1.1.2 Tumor scans during the study**

The first on-study scan assessment should be performed at 6 weeks ( $\pm 2$  weeks; starting from cycle 1 day 1). Subsequent tumor scans should be performed every 6 weeks ( $\pm 2$  weeks) or more frequently if clinically indicated. Scan timing should follow calendar days and should not be adjusted for delays in cycle starts.

All supplemental imaging must be collected.

Objective response should be confirmed by repeat scan performed at least 4 weeks after the first indication of a response is observed. Patients will then return to the regular scan scheduled, starting with the next scheduled time point. Patients who receive additional scans for confirmation do not need to undergo the next scheduled scan if it is fewer than 4 weeks later; scans may resume at the subsequent scheduled time point.

When radiological disease progression is identified by the investigator in clinically stable patients, disease progression is to be confirmed by another set of scans performed 4 to 8 weeks later, per iRECIST guidelines in section [8.1.1.5](#).

If disease progression is not confirmed, clinically stable patients are to continue study interventions until progression is confirmed. Patients are to return to their regular scan schedule. If the next scheduled scan will occur in less than 4 weeks, this scheduled scan may be skipped.

If disease progression is confirmed, study interventions will be discontinued. Exceptions are detailed in section [8.1.1.5](#).

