10.7 Cycle

Cycle number will be taken from the database. Unscheduled visits will be in listings only and identified with a numbering system that reflects the cycle they occur in by comparing the visit date against the scheduled visits and numbering in order of unscheduled visit e.g. Unscheduled Cycle 1 Day 1.01, Unscheduled Cycle 1 Day 8.01 etc. Unscheduled visits occurring on the same day as other visits will be kept as separate records.

Tumor assessments are not performed regularly per cycle, these will be identified in the ADaM datasets by actual week of study by calculating (date of assessment – date of study start+1)/7 and rounding up.

Additionally for the purposes of summarizing by scheduled week, labels for assessments falling into the scheduled week of study will be derived e.g. 'Week 6 assessment (Weeks 4 to 8)', 'Week 12 assessment (weeks 10 to 14)' etc., by assigning the assessments within the protocol specified window of every 6 weeks \pm 2 weeks. Labels for assessments falling outside of the assessment windows would be labelled 'Not Assigned'. In the case of multiple tumor assessments in a time window, evaluable assessments closest to the planned assessment time (or the closest non-evaluable assessment if all non-evaluable) will be considered the scheduled assessment. In the case of two assessments within a window being exactly the same distance from the centre of the window, the earliest assessment will be assigned as the scheduled assessment. Contributing assessments (e.g. target lesion assessment) should be labelled consistently with the overall tumor assessment.

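### SAP 12.7.6 footnote a reduces one missed scan to a bare 12 weeks; used as an upper limit, it censors single-missed-scan progressions that the table counts as PFS events

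*SAP*

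**What the plan says.** - **Event rule.** The PFS table in protocol 9.3.3.2 has a row for "Progression or death after one missed adequate tumor assessment", which is an event at the earlier of the two dates. The next row censors at the last evaluable assessment when more than one was missed. SAP 12.7.6 repeats both rows.
- **How the SAP identifies it.** Footnote a in SAP 12.7.6 hangs on the one-missed row only and reads, after its opening verb, "12 weeks between the date of last evaluable tumor assessment and the date of the event". The row for more than one missed carries no figure. The matching rows for DoR and iDoR in SAP 12.7.4 carry none either.
- **Schedule.** Protocol 8.1.1.2: "Subsequent tumor scans should be performed every 6 weeks", with a window of ±2 weeks, on calendar days and not shifted when cycles are delayed.
- **Permitted omissions.** The same section says "Patients who receive additional scans for confirmation do not need to undergo the next scheduled scan if it is fewer than 4 weeks later", and, after an unconfirmed progression, "If the next scheduled scan will occur in less than 4 weeks, this scheduled scan may be skipped".
- **Windows.** SAP 10.7 derives scheduled-week labels (weeks 4–8, weeks 10–14 and so on) "by assigning the assessments within the protocol specified window of every 6 weeks", with the ±2-week allowance. A scan that misses every window gets the label Not Assigned.
- **Patients with no post-baseline scan.** The no-event row of the SAP table censors at the last evaluable assessment "or first date of study treatment if no post-baseline tumor assessments". A separate row makes death before any progression assessment an event at the date of death.

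**The concern.** The tables count missed scans, whereas the footnote measures elapsed time, and it is the only text that makes the one-missed row programmable. Twelve weeks is twice the scan interval, so it fits one missed scan only if both surrounding scans fall the same number of days from plan. The schedule does not require that.

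A programmer who uses 12 weeks as the ceiling of the one-missed row will send longer gaps to the row below. Those progressions are then censored at the last scan although only one scan was missed. Removing events in this way tends to overstate PFS and iPFS. DoR and iDoR would be affected too if the same cut were carried over. These endpoints are still to be reported, because SAP 6.1 drops only the exploratory ones after the August 2023 futility analysis.

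**Working it through.** **1. Inputs.** Scan interval 6 weeks = 42 days and window ±14 days (protocol 8.1.1.2, SAP 10.7); footnote value 12 weeks = 84 days (SAP 12.7.6).

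**2. The footnote's figure.** The planned gap with m missed scans is 42(m + 1) days. For m = 1 this is 84 days = 12 weeks, which reproduces the footnote with no window.

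**3. Gaps the windows allow.** Let the two scans fall d1 and d2 days from plan, each within ±14. The gap is 42(m + 1) + d2 − d1.
- One missed: 84 ± 28 = 56–112 days (8–16 weeks).
- Two missed: 126 ± 28 = 98–154 days (14–22 weeks).

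These ranges need no assumption about how timing is distributed. They overlap at 14–16 weeks.

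**4. A worked case.** Scan at week 4 (week-6 window), week-12 scan missed, progression at week 20 (week-18 window). One scan was missed, so the table says event. The gap is 20 − 4 = 16 weeks, so a 12-week ceiling censors the patient at week 4.

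**5. Share affected under the ceiling.** Assume d1 and d2 are independent and uniform on whole days within ±w. The gap exceeds 84 days when d2 > d1, so the share is (1 − 1/(2w + 1))/2.

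| w (days) | One-missed gaps over 84 days |
|---|---|
| 0 | 0% |
| 3 | (1 − 1/7)/2 = 42.9% |
| 7 | (1 − 1/15)/2 = 46.7% |
| 14 | (1 − 1/29)/2 = 48.3% |

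**6. Other single limits, at w = 14 (29 × 29 = 841 pairs).**
- 14 weeks (98 days): 105/841 = 12.5% of one-missed gaps are longer, and 0.1% of two-missed gaps are within it.
- 16 weeks (112 days): no one-missed gap is longer, and 120/841 = 14.3% of two-missed gaps are within it.

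**7. Effect on the Kaplan-Meier summaries.** The documents give no missed-scan rate, so 5%, 10% and 20% per scan are assumed. The simulation used 60,000 patients per scenario, exponential PFS with a median of 3 or 6 months, progression found only at scans, independent missed scans and offsets uniform within ±3 or ±14 days. Where no post-baseline scan existed, gaps were measured from, and censoring placed at, the first treatment day. The 84-day ceiling was compared with a count of missed windows on the same patients.

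| Missed per scan | Events wrongly censored | Rise in 6-month PFS (points) | Rise in median (days) |
|---|---|---|---|
| 5% | 3.3–4.6% | 0.5–0.9 | 0–5 |
| 10% | 6.4–8.4% | 1.0–1.7 | 0–8 |
| 20% | 11.2–14.6% | 2.1–3.2 | 0–39 |

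The largest median shifts are jumps from one scan date to the next. They arise only at 20% missed with a 6-month median.

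**The case against.** - **The footnote is the definition.** Neither document otherwise says what a missed or adequate assessment is, and twice the scan interval is a simple elapsed-time rule that is right when scans are on time. The SAP 10.7 labels were made for summaries by scheduled week, so a window count is partly a reviewer's preference. This stands in part: a time rule is legitimate. But 12 weeks leaves out a window that both documents state, and the rows are still worded as counts of assessments.
- **The SAP never says that more than 12 weeks means censored.** True. The upper-limit reading is inferred. It is, however, the only reading that keeps the next row meaningful without adding a cut the SAP does not state. Taken as at least 12 weeks, the footnote would also take in every two-missed gap (minimum 98 days). Taken as exactly 84 days, it would match only 3–14% of one-missed gaps. An 18-week cut for two missed appears nowhere. A reader might infer that the SAP is open to several equally good readings; these are too strained to support that.
- **The effect is small.** This stands. At 50–57 patients per cohort and 6-month PFS of 25–50%, the binomial standard error is √(p(1 − p)/n), about 6–7 points, against a shift of 0.5–3.2. The analysis is descriptive, and protocol 9.3.1 foresees a time-to-event sensitivity analysis if missing data warrant it. But the shift is systematic, and the rule is cheap to state before database lock.

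**Conclusion.** The point holds as a defect in a stated rule. Used as an upper limit, footnote a contradicts the one-missed row it is meant to identify, in the SAP and in the protocol, for every in-window gap from more than 12 up to 16 weeks. The 8–16 and 14–22 week ranges follow from the documents alone. The 43–48% share rests on uniform, independent timing and falls to 0% if scans are exactly on schedule. The Kaplan-Meier shifts rest further on assumed missed-scan rates and exponential PFS.

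Two larger claims are tempting and not supported.
- **Baseline-scan reference.** With no post-baseline scan, one could measure the gap from a baseline scan up to 28 days before treatment, which raises the share over 84 days to 87% and the 6-month shift to as much as 4.3 points. The same table uses the first treatment day for patients with no post-baseline scan, and the protocol's amendment summary (change 18) chose that day to avoid negative times. Deaths before any progression assessment are also settled by their own row, so only progressions are open.
- **Wider reach.** Nothing here touches the primary ORR or the futility rule. Only PFS and iPFS are affected, and DoR and iDoR if the same cut is applied there.

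This is a correction that should be made, with modest expected effect.

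**What to change.** Replace footnote a with a count of consecutive scheduled windows (SAP 10.7 labels) that closed without an evaluable scan between the last evaluable scan and the event. One is an event; two or more is censored at the last evaluable scan. State also that:

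1. A window still open at the event is not missed. Example: last scan day 42, week-12 window (days 70–98) empty, death day 130 inside the week-18 window (days 112–140). One window closed empty, so this is an event, although the gap is 130 − 42 = 88 days.
2. An evaluable scan labelled Not Assigned is the last evaluable scan and restarts the count.
3. Scans that protocol 8.1.1.2 allows to be skipped are not missed. Example: response day 35, confirmation day 63, week-12 scan (day 84, 21 days later) skipped, week-18 scan missed, progression day 168. One scan was missed, although the gap is 168 − 63 = 105 days.
4. The existing row on death before any progression assessment takes precedence, so deaths with no post-baseline scan stay events.
5. For progression with no post-baseline scan, windows are counted from week 6. If two or more were missed, censoring is at the first day of study treatment, as in the no-event row. Censoring at a baseline scan would give a negative time.

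Refer to the same count from SAP 12.7.4 for DoR and iDoR.

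A simpler alternative is an explicit at-most operator with a limit of 16 weeks (112 days). It censors no in-window one-missed progression but keeps about 14% of two-missed ones as events at ±14 days.

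The cost is a few lines of SAP text and programming, including a flag for permitted skips. The window labels are already derived and no new data are needed.
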